**2. Visits to adjust study drug (week 4 and week 8):** A blood sample (30 ml) will be collected at weeks 4 and 8 to measure CBC, CMP and FT concentrations. The time frame for follow-ups will be within a week of the designated follow up time. Dose of clomiphene will be adjusted to keep FT between 12 and 16 ng/dL (mid-normal for healthy young men). If FT is <12 ng/dl, then the dose of CC will be increased by 25mg/week. If FT is >16 ng/dl, then the dose will be reduced by 25mg/week. The blood samples for dose adjustment will be taken on Wednesday or Friday. Patients in both clomiphene and placebo groups will be told that their tablet quantities may vary during the study. If the number of pills of a patient in the clomiphene group is changed, a similar change will be made in the number of placebo tablets in the next patient in placebo group.

**3. Week 12:** The participants will come fasting and have blood drawn for research labs, CBC, CMP, SHBG, LH, FSH total and free T (45 ml). Waist circumference and testicular size will be measured. Gynecomastia will be assessed. Subjects will then be discharged from the study.

The following study termination criteria will be applied:-

- Adverse events considered by the PI to be associated with the use of the study drug
- Suspected thromboembolic event, including pulmonary embolism. Subjects who have a thromboembolic event ruled out may reinstate treatment
- Hemoglobin of 18 g/dL or higher, or a hematocrit of 54% or higher
- Visual changes which may be prolonged and possibly irreversible. Subjects will be advised to stop drug and be referred to an ophthalmologist.
- The subject requests to be withdrawn from the study

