**Data Analysis:** The focus of the proposed research is to evaluate the efficacy of clomiphene treatment on T concentrations in young obese post-pubertal males. Transformations of the data in order to meet statistical assumptions may be considered. The results will be computed as mean  $\pm$  standard deviation (SD). The primary endpoint of the study is to detect a difference in FT concentrations after treatment with clomiphene for 12 weeks. There are no prior studies analyzing the effect of clomiphene in young males with HH. However, studies in middle aged men with obesity related HH and use of clomiphene or its isomer, enclomiphene have shown an increase in FT concentrations by 150%(21, 43). Change in FT concentrations following clomiphene or placebo for 12 weeks will be compared among the groups by unpaired *t*-test. Conservatively estimating a difference in FT concentrations of 50%, a sample size of 15 patients per treatment group (assuming a drop-out rate of 20%) should provide adequate power( $\beta = 0.8$ ) to detect a significant difference ( $\alpha = 0.05$ ), provided the standard deviation of the residuals is not greater than 40%. Thus 30 obese subjects with HH (15 patients each in clomiphene and placebo groups) will be sufficient. For baseline comparisons with men without HH, we will recruit 30 eugonadal obese and 30 lean males. Thus there will be 90 subjects in the study.

**Secondary End Points:** The secondary endpoints for the study will be comparison of the relative change from baseline in HOMA-IR and inflammatory mediators after clomiphene or placebo. These parameters will also be compared between obese and lean males at baseline. We have previously shown that obese men with HH have 36% higher insulin resistance than eugonadal men. Estimating a difference in HOMA-IR of 20%, a sample size of 30 patients per treatment group should provide adequate power( $\beta = 0.8$ ) to detect a significant difference ( $\alpha = 0.05$ ), provided the standard deviation of the residuals is not greater than 25%.

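### The termination list does not say whether drug or participation ends; read by its heading, it gives up week-12 outcomes and leaves a completers comparison by default

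*Combined protocol and SAP*

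**What the plan says.** The list at the end of STUDY DESIGN, after the Week 12 visit, opens with "The following study termination criteria will be applied". Its five bullets do not all describe the same consequence:

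- Drug-related events: "Adverse events considered by the PI to be associated with the use of the study drug". No consequence is given beyond the heading.
- Suspected thromboembolism, with the addition "Subjects who have a thromboembolic event ruled out may reinstate treatment". This concerns treatment.
- Laboratory limits: "Hemoglobin of 18 g/dL or higher, or a hematocrit of 54% or higher". No consequence is given beyond the heading.
- Visual changes, with the addition "Subjects will be advised to stop drug and be referred to an ophthalmologist". This also concerns treatment.
- "The subject requests to be withdrawn from the study". This concerns participation.

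Nothing in the protocol provides for an early-termination sample, or for a week-12 sample once a criterion has been met.

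The Data Analysis paragraph gives one primary analysis: "Change in FT concentrations following clomiphene or placebo for 12 weeks will be compared among the groups by unpaired" t-test. Drop-out appears only in the sample size, "a sample size of 15 patients per treatment group (assuming a drop-out rate of 20" per cent). No analysis set, missing-data rule or sensitivity analysis is named.

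**The concern.** Stopping a drug and leaving a trial are different events, and only the second has to cost the outcome. Under a heading that ends study participation, a site could reasonably discharge a man at week 4 or 8 and never draw his week-12 blood. The reasons for discharge include one that is drug-related by definition, so the missing values may be related to treatment and the comparison of those who remain is no longer the randomised one.

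This goes beyond an unwritten missing-data rule, because a paragraph added at analysis cannot recover samples that were never taken. The secondary endpoints are the most exposed. FT is also measured at weeks 4 and 8, but the research samples for HOMA-IR and the inflammatory mediators are scheduled only at day 0 and week 12, so a man who leaves early has no post-baseline value at all. The Significance section says the trial is meant to yield preliminary efficacy data and to inform later designs, so the size of the estimate matters as well as its p-value.

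**Working it through.** **1. Reproduce the plan's sample size.** Inputs from Data Analysis: difference 50%, SD 40%, alpha 0.05 (taken as two-sided, since this is not stated), power 0.80, drop-out 20%.

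- Standardised difference: 50/40 = 1.25.
- Exact (noncentral) t power: 11 per arm gives 0.796; 12 per arm gives 0.833. So 12 are needed.
- Allowing for drop-out: 12/(1 − 0.20) = 15 per arm, the stated figure.

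The arithmetic counts a man who drops out as giving no primary data. That fits a completers analysis, although the plan does not say so.

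**2. Loss of numbers is not the main problem.** Power is 0.833 at 12 v 12. If all six expected drop-outs (20% of 30) were on clomiphene, it would be 0.809 at 9 v 15. The question is selection.

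**3. Illustrate the selection.** The documents give no counts or mechanism, so the following are assumptions: 15 per arm, normal changes with mean 50 (clomiphene) and 0 (placebo), SD 40, *k* = 2 or 3 men lost on clomiphene and none on placebo (40,000 simulated trials).

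Start with the limiting case, in which exactly the highest responders are lost. The estimated difference is 40.9 (*k* = 2) or 36.9 (*k* = 3), a shift of 9.1 or 13.1 points. If loss depends on a variable correlated ρ with response, the expected shift is ρ times the limiting shift:

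| Assumed ρ | 2 lost | 3 lost |
|---|---|---|
| 0.3 | 0.3 × 9.1 = 2.7 | 0.3 × 13.1 = 3.9 |
| 0.5 | 0.5 × 9.1 = 4.6 | 0.5 × 13.1 = 6.6 |
| 0.7 | 0.7 × 9.1 = 6.4 | 0.7 × 13.1 = 9.2 |

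Direct simulation at ρ = 0.5 gave estimates of 45.4 and 43.4, that is, shifts of 4.6 and 6.6. The range is therefore about 3 to 9 points. It is downward if high responders leave and upward if low responders leave.

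**4. Price the remedy.** Suppose instead that the 2 or 3 men stop drug, are measured at week 12, and are back at baseline FT on average.

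- Difference: 50 × 13/15 = 43.3, or 50 × 12/15 = 40.0.
- Simulated power: 0.79 or 0.71.

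Both powers are below the 0.833 at 12 per arm, and below the 0.873 for a purely random loss of three men from one arm (12 v 15).

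**The case against.** The strongest reply is that the text is ambiguous and does not command men to leave. Two bullets speak of treatment only, no sentence cancels a week-12 draw, and none restricts the analysis to completers. That stands. A reader might infer that every man who meets a criterion leaves the trial, but the bullets do not support that. The completers analysis is what the stated test yields by default; it is not a written rule.

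Four further inferences are tempting and also fail:

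- **Losses fall in the clomiphene arm.** All investigators other than the research nurse and pharmacist are blinded, so events can be attributed to study drug in either arm, and the other criteria apply to both.
- **The hematocrit rule removes high responders.** The documents nowhere link hemoglobin or hematocrit to FT. Hematocrit above 50% is excluded at entry. On-study blood counts are scheduled with FT, so a limit crossed at week 12 costs no primary value, and one crossed at week 4 or 8 has an FT from the same visit.
- **At most 3 of 15 are affected.** The 20% is an all-cause planning allowance, neither a count of terminations nor a ceiling.
- **The estimate could lie anywhere from 37 to 63.** Those values come from deleting exactly the three highest or three lowest responders. They are a limit, not an expectation.

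It can also be said that the finding of an effect is safe: the plan calls 50% conservative against a cited 150% rise, and at 150 points with SD 40 losing the top three still leaves about 150 − 13 = 137. That is fair for the significance test on FT. It does not answer the point about the size of the estimate, or about the secondary endpoints. Finally, an on-treatment question is defensible, but the plan would have to state it.

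**Conclusion.** The point holds as an inconsistency with a statistical consequence. The list mixes ending drug with ending participation; followed by its heading, it gives up week-12 outcomes for reasons that may be related to treatment; and the only stated primary test then compares completers.

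Whether bias would arise, in which direction and in which arm, cannot be derived from the documents. The 3 to 9 points is an illustration. It rests on the plan's 50-point difference and 40-point SD, on 2 or 3 losses confined to clomiphene, and on an assumed correlation of 0.3 to 0.7. With one man lost, the limiting shift is 50 − 45.0 = 5.0 points, and the same correlations give 1.5 to 3.5.

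A reader might also expect that keeping everyone to week 12 raises power from 0.83 at 12 per arm to 0.91 at 15. That would require men off drug to keep the full effect. If they return to baseline, power falls to 0.79 or 0.71. The reason to change is to protect the randomised comparison. It is a cheap improvement, best made before men start to leave.

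**What to change.** 1. Reconcile the heading with the bullets, so that each criterion states whether drug or study participation ends. The clinical criteria themselves are for the sponsor.
2. State that a man who stops drug still attends the week-12 visit and blood draw, including the research samples, unless he withdraws consent.
3. Make the primary comparison on all randomised men in their assigned arm, and name the estimand for men who stop drug. Where the week-12 FT is missing, use the week-4 and week-8 values in a mixed model. That model assumes the loss is explained by the arm and the FT values already observed, and it cannot help HOMA-IR or the inflammatory markers, which have no interim samples. Item 2 therefore matters most.
4. Keep the unpaired t-test in completers, or on treatment, as a sensitivity analysis.

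The cost is protocol wording, a few week-12 visits for men off drug, and a diluted effect: about 43 to 40 points in place of 50 if 2 or 3 of 15 clomiphene men are back at baseline, with power of about 0.79 to 0.71.

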### **Laboratory measurements:-**

**Measurement in research laboratory:** Insulin concentrations will be determined using an ELISA kit from Diagnostic Systems Laboratories Inc. (Webster, TX). Glucose levels will be measured in plasma by YSI 2300 STAT Plus glucose

analyzer (Yellow Springs, Ohio). HOMA-IR will be calculated from fasting insulin and glucose level using the formula: [fasting insulin (mU/l) X fasting glucose (mmol/l)]/22.5. TNF- $\alpha$ , IL-1 $\beta$  and CRP concentrations will be measured by ELISA. FFA will be measured by a colorimetric assay. MNC will be isolated by Ficoll-hypaque method.

Quantification of mRNA expression of SOCS-3, IKK-  $\beta$ , and PTEN will be done by RT-PCR as previously published (4, 39, 40). Insulin like factor 3 and inhibin B will be measured by ELISA.

**Measurements in commercial laboratory:** T is largely bound to SHBG (44%) and albumin (54%). Hence, total T does not reflect the bio-availability of T at the cellular level (41). Obesity is associated with lower SHBG concentrations. It is therefore important to measure FT concentrations in obese males to get an accurate assessment of gonadal status. Reliable assays for FT were not widely available until recently. In our study, we will measure T by the gold standard method, liquid chromatography tandem mass spectrometry (LC-MS/MS) (42). FT will be separated by equilibrium dialysis. SHBG, LH and FSH will be measured by immunoassays. CBC and CMP will be measured by well established clinical assays. The assays will be performed by Quest Diagnostics. We have previously published many studies in which measurements of serum T on our study subjects were done by Quest Diagnostics (1, 3, 5, 6, 9).

**Data Analysis:** The focus of the proposed research is to evaluate the efficacy of clomiphene treatment on T concentrations in young obese post-pubertal males. Transformations of the data in order to meet statistical assumptions may be considered. The results will be computed as mean  $\pm$  standard deviation (SD). The primary endpoint of the study is to detect a difference in FT concentrations after treatment with clomiphene for 12 weeks. There are no prior studies analyzing the effect of clomiphene in young males with HH. However, studies in middle aged men with obesity related HH and use of clomiphene or its isomer, enclomiphene have shown an increase in FT concentrations by 150%(21, 43). Change in FT concentrations following clomiphene or placebo for 12 weeks will be compared among the groups by unpaired *t*-test. Conservatively estimating a difference in FT concentrations of 50%, a sample size of 15 patients per treatment group (assuming a drop-out rate of 20%) should provide adequate power( $\beta = 0.8$ ) to detect a significant difference ( $\alpha = 0.05$ ), provided the standard deviation of the residuals is not greater than 40%. Thus 30 obese subjects with HH (15 patients each in clomiphene and placebo groups) will be sufficient. For baseline comparisons with men without HH, we will recruit 30 eugonadal obese and 30 lean males. Thus there will be 90 subjects in the study.

**Secondary End Points:** The secondary endpoints for the study will be comparison of the relative change from baseline in HOMA-IR and inflammatory mediators after clomiphene or placebo. These parameters will also be compared between obese and lean males at baseline. We have previously shown that obese men with HH have 36% higher insulin resistance than eugonadal men. Estimating a difference in HOMA-IR of 20%, a sample size of 30 patients per treatment group should provide adequate power( $\beta = 0.8$ ) to detect a significant difference ( $\alpha = 0.05$ ), provided the standard deviation of the residuals is not greater than 25%.

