### **STUDY DESIGN:-**

**Screening Day (part of study):** All subjects will have completed the following procedures prior to participating in the study:-

1) Medical History; 2) Physical Exam: testicular volume will be measured by an orchidometer (38); 3) Informed consent; 4) Baseline lab (30 ml) draw to measure CBC, comprehensive metabolic panel (CMP that includes liver and kidney function tests), total and free T, SHBG, LH and FSH. All labs will be drawn in the fasting state in the morning before 10am. All laboratory samples will be tested in the Endocrine laboratory in Doisy Hall Room 204.

**Study visits for males with normal FT:** The participants will come fasting and have blood drawn for research labs (insulin, glucose, inflammation). They will then be discharged from the study.

**Study visits for obese males with HH:** These subjects will enter a double blind randomized placebo controlled trial. Subjects who qualify and consent to take part in the study will be assigned a number by a computerized random number generation program and will be randomized (1:1) to receive either clomiphene or placebo. An unblinded research nurse and pharmacist will administer study product, all other investigators and the study participants will be blinded. This number will be used as the study subject ID. A master list of subject name and study ID will be kept under lock and key to protect patient identifiers. Only the assigned research nurse will have access to the randomization list.

**1. Visit day 0:** The participants will come fasting and have blood drawn for research labs (insulin, glucose, CRP; 45 ml). Waist circumference will be measured. They will be given a supply of clomiphene or placebo pills containing cellulose. Clomiphene citrate is available as 50 mg tablets and has a half life of 5-7 days. The starting dose of clomiphene will be 25mg on Monday, Wednesday and Friday mornings. All subjects will be given a pill container that will have separate boxes for different days of the week.

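### HOMA-IR and the inflammatory mediators are compared between arms as relative change, with no named test and no baseline covariate; log-scale ANCOVA on the same samples would usually be more precise, by an amount the documents do not fix

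*Combined protocol and SAP*

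**What the plan says.** In the combined protocol and SAP, the Secondary End Points paragraph sets the treatment comparison as "comparison of the relative change from baseline in HOMA-IR and inflammatory mediators after clomiphene or placebo". It gives no test for it. The only test named is for the primary endpoint, in the Data Analysis paragraph: "Change in FT concentrations following clomiphene or placebo for 12 weeks will be compared among the groups by unpaired *t*-test". No regression model or baseline covariate appears anywhere.

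On scale, the Data Analysis paragraph says "Transformations of the data in order to meet statistical assumptions may be considered", without saying for which endpoints, to what scale or on what trigger. Summaries are arithmetic: "The results will be computed as mean" and SD.

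The HOMA-IR sample size takes a 20% difference and 30 men per treatment group, "provided the standard deviation of the residuals is not greater than 25" percent. The model behind those residuals is not defined. The randomised arms have 15 men each.

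Both blood draws are planned. For day 0: "The participants will come fasting and have blood drawn for research labs (insulin, glucose, CRP; 45 ml". For week 12: "The participants will come fasting and have blood drawn for research labs, CBC, CMP, SHBG, LH, FSH total and free T (45 ml". The day-0 list names insulin, glucose and CRP. For the other mediators, a day-0 value is implied by the endpoint itself.

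**The concern.** Relative change divides the week-12 value by a single day-0 value that carries day-to-day and assay noise. This has three consequences.

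- The measure is right-skewed, and HOMA-IR is itself a product of two assays. If within-man log SD is *w* at each visit and nothing truly changes, mean percent change is still exp(*w*²) − 1: about +6.5% at *w* = 0.25 and +17% at *w* = 0.4. Reported as mean and SD, that looks like worsening within an arm.
- A chance difference between arms at day 0 is left in the comparison, and with 15 men per arm such differences are not small.
- With neither test nor scale fixed, both can be chosen after the data are seen.

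Aims 2.2 and 2.3 rest on these comparisons, and the Significance section says the results will inform future trials.

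**Working it through.** **1. The plan's own figure.** For a 20% difference, SD 25%, two-sided 0.05 (sidedness assumed) and 80% power, d = 20/25 = 0.8 and n = 2(1.96 + 0.84)²/0.8² ≈ 24.5, so 25 per group. Multiplying by 1.2 for the 20% dropout (stated only for FT) gives the plan's 30. By noncentral t, power is 0.861 at 30 per group, 0.562 at the 15 per arm actually randomised, and 0.466 at 12 completers (15 × 0.8).

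**2. What the covariate does on the plan's inputs.** Let σ be the SD at each visit (assumed equal) and ρ the day-0 to week-12 correlation. The SD of change is σ√(2(1−ρ)) and the ANCOVA residual SD is σ√(1−ρ²), so their ratio is √((1+ρ)/2). Reading 25% as the SD of change:

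- ρ = 0.5: 25 × 0.866 = 21.65, d = 0.924
- ρ = 0.8: 25 × 0.949 = 23.72, d = 0.843

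At 15 per arm, noncentral t with 27 df and variance factor 1 + 1/(2n−4) gives 0.668 and 0.589, gains of 10.6 and 2.7 points over 0.562. Simulated power (40,000 runs per cell), change score / ANCOVA:

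| ρ | 15 per arm | 12 per arm |
|---|---|---|
| 0.5 | .561 / .669 | .464 / .558 |
| 0.6 | .564 / .643 | .462 / .532 |
| 0.7 | .565 / .617 | .464 / .505 |
| 0.8 | .559 / .585 | .464 / .486 |
| 0.9 | .562 / .568 | .468 / .469 |
| 0.95 | .560 / .554 | .465 / .457 |

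The covariate alone therefore adds 2.2 to 10.8 points at ρ from 0.8 to 0.5 and 0.1-0.6 at 0.9, and loses 0.6-0.8 at 0.95. With the log scale included and a true ratio of 0.80, the simulated gain over percent change at ρ = 0.5 is 11.9 points (.647 to .766, 15 per arm).

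If 25% is instead already a baseline-adjusted residual SD, then for ρ = 0.5 to 0.8 the change score has power .452-.523 at 15 per arm against about .55 for ANCOVA, and .367-.429 against about .45 at 12.

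**3. Lognormal check at the plan's 20% effect.** The between-man and within-man log SDs are assumptions. Power is for a t-test on percent change / log ANCOVA:

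| Between / within SD (ρ) | 15 per arm | 12 per arm |
|---|---|---|
| 0.4 / 0.25 (0.72) | .368 / .426 | .294 / .338 |
| 0.4 / 0.4 (0.50) | .159 / .219 | .133 / .179 |
| 0.5 / 0.25 (0.80) | .368 / .408 | .300 / .330 |
| 0.5 / 0.4 (0.61) | .160 / .211 | .135 / .172 |

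Gains are 3.0-6.0 points. With no true effect, rejection is .048-.051 for ANCOVA and .043-.049 for percent change.

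**4. Making the two sets of inputs agree.** A within-man log SD of 0.25-0.4 implies an SD of log change of 0.35-0.57 (× √2), well above 25%. Holding 25% gives a within-man SD of 0.25/√2 = 0.177. With between-man SD 0.4-0.5, ρ is then 0.84-0.89. Power at a 20% fall is .645 / .678 and .640 / .662 at 15 per arm, and .540 / .568 and .537 / .550 at 12. The gain is 1.3-3.3 points, or about 1-4 once simulation error is allowed for.

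**5. Chance imbalance.** In the lognormal cells, suppose nothing truly changes but one arm starts one standard error higher (19-30% in HOMA-IR). The percent-change difference then averages −4.7 to −14.0 points, while the ANCOVA ratio stays at 0.995-1.003. This is conditional on the imbalance having occurred, so it shows the same loss of precision from another side.

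**The case against.** The strongest reply is that no error has been shown. Relative change holds its type I error, the plan allows a transformation, the trial is described as preliminary, and its focus is testosterone. No correlation, log SD or SD of change for treated men appears in the documents. The 20%/25% inputs may even belong to the baseline comparison of groups of 30 rather than to the treatment comparison. On the version of the inputs that fits together best (step 4), the gain is small.

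Most of this stands, and it limits the size claimed. It does not remove the point: permission to transform supplies neither a test nor a covariate, and the remedy uses data that relative change already requires.

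A reader might draw four stronger conclusions that the documents do not support.

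- **That relative change biases the treatment comparison.** Under 1:1 randomisation it does not.
- **That about 13 points of power are being lost.** The largest simulated gain in the lognormal cells, 13.3 points, needs a 30% fall with ρ = 0.5 and 15 per arm. The plan states 20%.
- **That the same gain applies to cytokines, CRP, FFA and mRNA.** No SD or effect is given for them.
- **That ANCOVA rescues the claimed 80% power.** The best 20%-effect result at ρ of 0.5 or more is .766 at 15 per arm. The mismatch between 30 per treatment group and arms of 15 is a separate matter.

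**Conclusion.** The point holds as a modest, nearly free gain in precision together with a gap in prespecification. The direction is secure for moderate correlations; the size is not. The range is roughly 1 to 12 points of power at the plan's 20% effect, depending mainly on the unknown correlation, and the lower part applies if the plan's 25% is combined with a between-man log SD of 0.4-0.5. At a correlation of 0.9 or more there is almost nothing to gain. These figures assume a t-test on percent change as comparator (the plan names none), equal variance at both visits, and lognormal data where simulated.

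**What to change.** In the Secondary End Points paragraph, state that HOMA-IR and each inflammatory mediator will be analysed by ANCOVA of the log week-12 value on treatment and log day-0 value, in men with both values. Report the clomiphene/placebo ratio with 95% CI, and geometric means per arm in place of mean percent change. Say plainly that this does not deliver 80% power for HOMA-IR at 15 per arm. Leave the primary FT t-test as it is.

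Optionally, if any values may fall below an assay limit, prespecify one simple substitution and a sensitivity run with another. The choice matters: with 10-30% of day-0 values below the limit and a true ratio of 0.70, limit/2 gives 0.67-0.70 and limit/√2 gives 0.71-0.75 (between-man SD 0.5, within-man SD 0.4 assumed).

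The cost is one paragraph of wording and one degree of freedom (27 instead of 28 at 15 per arm), with no new visit, sample or assay. At a correlation near 0.95 it would lose less than 1 point of power in the simulations.

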## **APPROACH**

The study will be conducted at the division of Endocrinology, Saint Louis University. Young males between the ages of 18-45 years will be recruited for the study. A total of 90 males will be recruited: 30 obese males (defined as  $\geq$ 30 kg/m^2) with HH, 30 obese males with normal FT concentrations and 30 lean males (<25 kg/m^2) with normal FT concentrations.

**Hypogonadal males:** 30 male subjects with HH will be recruited into the study. HH will be defined as subnormal FT concentrations along with normal or low LH concentrations ( $\leq$ 10 IU/L). We will define subnormal FT as <6.5 ng/dl. Subjects with subnormal FT and high LH (>10 IU/L) will not be recruited into the study. Obese subjects will be randomized to receive clomiphene or placebo (15 subjects each) thrice a week for 12 weeks.

**Eugonadal men:** 30 obese and 30 lean males with normal FT ( $\geq$ 6.5 ng/dl) will also be recruited in the study to serve as comparison groups. They will not be treated clomiphene.

**INCLUSION CRITERIA FOR THE STUDY:** Males with age 18-45 years inclusive will be recruited. Subjects with type 2 diabetes on anti-hyperglycemic drugs (including insulin) will be allowed as long as they are on stable doses of these compounds for at least 6 weeks. The doses of anti-hyperglycemic can be changed if the subject has hypoglycemia or hyperglycemia. A record of all the changes in the doses of the anti-diabetic drugs will be kept.

**EXCLUSION CRITERIA FOR THE STUDY:** 1) Use of androgens, clomiphene, hCG, aromatase inhibitors or over the counter health supplements which contain androgens currently or in the past 6 months; 2) Hematocrit > 50%; 3) Congestive heart failure; 4) currently suffering from depression; 5) type 1 diabetes; 6) Hepatic disease (transaminase > 3 times normal) or cirrhosis, or a history of liver dysfunction; 7) Renal impairment (eGFR < 30 ml/min/1.73m^2); 8) HIV or Hepatitis C positive status; 9) Participation in any other concurrent clinical trial; 10) currently suffering from foot ulcer, significant periodontal disease or any other chronic infectious condition 11) known allergy to clomiphene 12) uncontrolled adrenal or thyroid dysfunction 13) presence of an organic intracranial lesion e.g. pituitary tumor 14) history of cataracts 15) history of venous thromboembolic disease (i.e. deep vein thrombosis or pulmonary embolism).

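### HOMA-IR power is claimed for 30 patients per treatment group, but each arm has 15; on the plan's own inputs the clomiphene–placebo comparison has 47–56% power, not 80%

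*Combined protocol and SAP*

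**What the plan says.** The Secondary End Points paragraph of the Data Analysis section first defines the endpoint as the relative change from baseline in HOMA-IR and inflammatory mediators on clomiphene or placebo. It adds that these parameters will also be compared between obese and lean men at baseline, and cites 36% higher insulin resistance in obese men with HH than in eugonadal men. The power statement follows: "Estimating a difference in HOMA-IR of 20%, a sample size of 30 patients per treatment group should provide adequate power". Its condition on variability is "provided the standard deviation of the residuals is not greater than 25" percent. Power is printed as beta = 0.8, which can only sensibly mean 80% power, and alpha is 0.05.

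The size of the treatment groups is fixed elsewhere:

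- APPROACH, hypogonadal males: "Obese subjects will be randomized to receive clomiphene or placebo (15 subjects each) thrice a week for 12 weeks".
- STUDY DESIGN: these men "will be randomized (1:1) to receive either clomiphene or placebo".
- Data Analysis, primary endpoint: "Thus 30 obese subjects with HH (15 patients each in clomiphene and placebo groups) will be sufficient". The drop-out allowance also stands there: "a sample size of 15 patients per treatment group (assuming a drop-out rate of 20" percent).

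**The concern.** Within one section, the term treatment group carries 15 men in the primary-endpoint calculation and 30 in the HOMA-IR calculation. Only 15 agrees with the design. Thirty is the total randomised, and also the size of each baseline cohort (obese with HH, obese eugonadal, lean). The two eugonadal cohorts are not treated, so they are not treatment groups.

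HOMA-IR is the first-named secondary endpoint and part of Aim 2.2, and the second hypothesis is that clomiphene reverses the reduced insulin sensitivity. The Significance section says the results will inform future trials. If the comparison shows no difference, a reader of the plan would credit it with 80% power and could take the result as evidence against a metabolic effect. With the actual arm sizes, that inference would not be justified.

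**Working it through.** **Inputs**

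- Difference 20% and SD 25% (Secondary End Points), so d = 20/25 = 0.8.
- Alpha 0.05 (same paragraph). Sidedness is not stated; two-sided is assumed.
- Test: unpaired t-test. It is named for free testosterone; none is named for HOMA-IR, so the same test is assumed.
- Arm size: 15 randomised (APPROACH; Data Analysis). With the primary endpoint's 20% drop-out, 15 × 0.8 = 12. HOMA-IR change needs the same week-12 fasting sample, so the same loss is a reasonable assumption.

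**Reproducing the plan's figure.** By the normal approximation, n per group = 2 × (1.96 + 0.842)² / d² = 2 × 7.85 / 0.64 = 24.5, so 25. The t-test needs 26. Thirty per group is therefore more than enough for 80% power if 30 per group are available. The exact figure of 30 also arises as 25 × 1.2 (a drop-out inflation), or on the log scale from ln(1.20) with SD 0.25. The calculation is sound for groups of 30; the fault lies in the groups it is attached to.

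**Power at the actual arm sizes.** The noncentrality parameter is d × √(n/2), with 2n − 2 degrees of freedom. The last column is d₈₀ × 25%, where d₈₀ is the standardised difference that gives 80% power by the t-test.

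| n per group | Noncentrality | Power, t-test | Power, normal approx. | Difference detectable with 80% power |
|---|---|---|---|---|
| 30 | 0.8 × √15 = 3.10 | 86.1% | 87.3% | 18.4% |
| 15 | 0.8 × √7.5 = 2.19 | 56.2% | 59.1% | 1.060 × 25 = 26.5% |
| 12 | 0.8 × √6 = 1.96 | 46.6% | 50.0% | 1.197 × 25 = 29.9% |

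**SD that would rescue the claim.** For 80% power at a 20% difference, the SD must not exceed 20/1.060 = 18.9% with 15 per arm, or 20/1.197 = 16.7% with 12, against the 25% the plan allows.

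**Sensitivity to what the plan leaves open** (12 to 15 per arm):

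- One-sided test: 60–69% (t-test), 62–71% (normal approximation).
- Log scale, ln(1.20), SD 0.25, two-sided t-test: 40–49%.
- Log scale, a 20% reduction (ln 0.80), SD 0.25, two-sided t-test: 55–66%.

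None of these reaches 80%.

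**Primary endpoint.** With a 50% difference and SD 40% (d = 1.25), 12 per arm give 83% power by the t-test, so the free-testosterone sample size holds.

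**The case against.** The strongest reply is that the sentence was meant for the baseline comparison. It directly follows the remarks on obese versus lean men and on the 36% difference between HH and eugonadal men. The 20% looks like a cautious discount from that 36%, just as the primary calculation discounts 150% to 50%. Thirty is the size of each cohort, and no drop-out is mentioned, which suits a single-visit comparison. Power there is about 86%, so the claim of adequate power would be true and the only error would be the label.

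This reading is plausible, but it does not rescue the text. The paragraph opens with change on clomiphene or placebo, and the preceding paragraph uses the same label for the 15-man arms, so a reader taking the words at face value will apply the 80% to the treatment comparison. If only baseline was meant, the treatment comparison of HOMA-IR has no power statement at all.

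Three further points stand as limits. If 20% and 25% were chosen for a cross-sectional difference, using them for relative change is an assumption; the documents give no SD for change. The 25% is a ceiling, so a smaller SD would raise power. The 20% drop-out is stated only for the primary endpoint. It is also fair that HOMA-IR is secondary and that the study describes its efficacy data as preliminary.

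**Conclusion.** The statement is wrong as written: the design does not provide 30 patients per treatment group. Power for clomiphene versus placebo on HOMA-IR is 56% if all 15 per arm are evaluable and 47% with 12. These figures assume that the plan's 20% difference and 25% SD apply to relative change, and that the test is a two-sided unpaired t-test at 0.05. The unstated sidedness, scale and drop-out move the figure, but no variant examined reaches 80%. Whether the author meant the treatment arms or the baseline cohorts decides which words are wrong; it does not change the power of the treatment comparison. The error is confined to a secondary endpoint and leaves the primary sample size intact.

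**What to change.** Replace the single power sentence with two, and name the test and its sidedness for HOMA-IR:

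1. Baseline comparison, HH versus obese eugonadal (or lean) men, 30 per group: about 86% power for a 20% difference with SD 25%.
2. Clomiphene versus placebo, 15 randomised and 12 expected completers per arm: 47–56% power for a 20% difference with SD 25%; the difference detectable with 80% power is about 30% with 12 completers.

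The sponsor should confirm which comparison the 20% and 25% were chosen for. If they were cross-sectional, the second sentence should say that they are carried over to relative change as an assumption. Presenting the treatment effect on HOMA-IR as an estimate with a confidence interval would suit this precision, but correcting the contradiction does not require it.

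The cost is two sentences in the Data Analysis section and a less favourable power figure for a secondary endpoint. Enrolment, randomisation, procedures and the primary analysis stay as they are.
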